## **12. ASSESSMENT OF SAFETY**

### **12.1. Safety Parameters**

The scope of safety monitoring is to assess the potential risks to the participants and ensure the safety of the participants during this trial. In order to monitor the data and safety, all necessary data including AE/SAE reports, safety reports (from Stemnion), subjects' medical/medication history, concomitant medication reports, review of subject conduct/compliance, soft and hard tissue evaluations at every visit, and dropout rates will be used and reviewed throughout the study. Serum chemistry including liver and kidney function, complete blood count, and urinalysis will be done at screening, Day 90, and Day 270. In women of child-bearing potential, a pregnancy test will be performed prior to enrollment and again at the last study visit (Day 270).

#### **12.1.1. Demographic/Medical History**

Complete medical history will be taken at screening. Interim history will be taken at each treatment and follow-up visit.

#### **12.1.2. Vital Signs**

Blood pressure, heart rate, temperature, and respiratory rate will be recorded at screening, baseline, and at each evaluation visit.

#### **12.1.3. Weight and Height**

Height and weight will be recorded at screening and weight will be recorded at Day 270.

#### **12.1.4. General Assessments**

A general assessment looking for allergic and potential toxic reactions will be made at each visit prior to treatment with study drug. The oral mucosa will be examined at each visit.

#### **12.1.5. Laboratory Assessments**

Blood (10 to 15 mL) and urine samples (3 to 5 mL) will be sent to a certified laboratory for hematology, blood chemistry, and urine tests at screening and at Days 90 and 270. If a subject has any laboratory value that was normal upon entry into the trial and becomes abnormal, the sponsor's Medical Monitor will review the data with the investigator to assess whether the laboratory value represents a safety concern.

#### **12.1.6. Hematology**

Complete blood count will be performed at screening and at Days 90 and 270. If a subject develops hemoglobin, hematocrit, or white blood cell count outside the normal range (as per the laboratory normal range values), that case will be reviewed by the sponsor's Medical Monitor. The Medical Monitor may determine that the subject will receive no further study drug treatment.

#### **12.1.6.1. Blood Chemistry**

Serum glucose, C-reactive protein, blood urea nitrogen, creatinine, electrolytes, HbA1c (at screening only), and liver function including bilirubin and hepatic enzymes will be measured at screening and at Days 90 and 270.

#### **12.1.6.2. Urinalysis**

Urinalysis will be performed at screening and at Days 90 and 270. If a subject develops hematuria or proteinuria after treatment is initiated, that case will be reviewed by the sponsor's Medical Monitor, who may determine that the subject will receive no further study drug treatment.

#### **12.1.6.3. Pregnancy Screen**

Urine pregnancy testing will be performed at screening and at the final visit (Day 270) on females of child-bearing potential using commercially available pregnancy tests.

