**Table 3: Study Design and Schedule of Assessments**

Evaluation	Treatment and Follow-up Period									
	Visit 1 Screening	Visit 2 Baseline (≤30 days from screening)	Visit 3/3b SRP (≤10 days from baseline)	Visit 4 Day 1 a (≤3 days from SRP)	Visit 5 Day 15 (±1 day)	Visit 6 Day 30 (±3 days)	Visit 7 Day 60 (±3 days)	Visit 8 Day 90 (±5 days)	Visit 9 Day 180 (±7 days)	Visit 10/EOS Day 270 (±7 days)
Informed Consent	X									
Pregnancy Test (female subjects)	X									X
Demographics	X									
Inclusion/Exclusion	X	X								
Dental History	X									
Medical History	X									
Vital Signs	X	X	X	X	X	X	X	X	X	X
Height and Weight	X b									X
Medical/Dental History Update g		X	X	X	X	X	X	X	X	X
Oral Exam	X	X	X	X	X	X	X	X	X	X
Randomization SRP d			X c X							
Full Mouth Plaque Index (FMPI)		X			X	X	X	X	X	X
Clinical Measurements (PD, CAL, BOP)	X				X	X	X	X	X	X
GCF Sampling		X			X			X e	X e	X
Serum Sampling		X			X			X	X	X
Microbial Sampling		X			X			X	X	X
Radiographs		X						X		X
General Labs	X f							X		X
Administration of Test Article				In-office treatments as scheduled in Figure 1						
Oral Hygiene Instruction g	X	X	X	X	X	X	X	X	X	X
Adverse Events g	X	X	X	X	X	X	X	X	X	X
Concomitant Medication g	X	X	X	X	X	X	X	X	X	X

BOP=bleeding on probing; CAL=clinical attachment level; EOS=end of study; FMPI=full-mouth plaque index; GCF=gingival crevicular fluid; HbA1c=glycated hemoglobin;

IWRS=interactive web response system; PD=pocket depth; SRP=scaling and root planing.

a The first in-office treatment may be performed on the same day as the last SRP visit. The last SRP may occur on Visit 3/3b, or as an Unscheduled Visit. The Unscheduled Visit may be combined with Visit 4. Product administration must occur within 3 days of the last SRP visit.

b Height is measured only at screening.

c Randomization occurs by IWRS after SRP has been completed.

d SRP may be initiated on the same day as the Baseline visit and may require more than one visit. Subjects with moderate to heavy deposits will typically have no more than two quadrants treated in a single SRP visit. Local anesthesia must be used for SRP.

[figure not shown]
e Sample is collected before treatment is applied.

f HbA1c is measured at screening only.

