## **8. SELECTION AND WITHDRAWAL OF SUBJECTS**

### **8.1. Subject Inclusion Criteria**

1. Provision of signed, written informed consent prior to participation in any study-related procedures.
2. Good general health as evidenced by the medical history.
3. Between 18 and 85 years of age at the time of informed consent signature.
4. Male or female.
5. Minimum of 18 teeth, excluding third molars.
6. Having moderate to severe periodontal disease according to American Academy of Periodontists (AAP) definition (at least 6 teeth with  $\geq 6$  mm PD and  $\geq 3$  mm CAL at baseline).
7. Having  $>30$  percent bleeding sites upon probing.
8. Willing to abstain from chewing gums and other mouth rinses for the study duration.
9. Ability and willingness to attend all study visits and comply with all study procedures and requirements.
10. Willingness to abstain from routine dental care.
11. For women with reproductive potential, willingness to use highly effective contraception (e.g., licensed hormonal contraception, intrauterine device, abstinence, or vasectomy in partner).

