9.5 Clinical Laboratory Evaluation

Blood is to be drawn and urine collected for laboratory analysis at Screening, and on Days 90 and 270. The following clinical laboratory parameters are to be assessed:

- Hematology: Complete blood count
- Blood chemistry: serum glucose, C-reactive protein, blood urea nitrogen, creatinine, electrolytes, HbA1c (at screening only), and liver function including bilirubin and hepatic enzymes
- Urinalysis: hematuria, proteinuria, pregnancy test (at screening and final visit only)

Tables will present continuous summary statistics for each lab parameter collected by visit and treatment group.

Laboratory values outside the normal range will be flagged as “high” or “low”. Percentage of subjects with values falling in high, normal, and low ranges will be summarized by lab parameter and visit, by treatment group.

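### Pregnancy is tested only at screening and Day 270, so the screening result can be up to 43 days old at the first dose and the second test comes after dosing ends

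*Protocol*

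**What the plan says.** Pregnancy is exclusion criterion 5 (protocol 8.2). Testing is described in five places, and they agree:

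- Protocol 12.1.6.3: "Urine pregnancy testing will be performed at screening and at the final visit (Day 270) on females of child-bearing potential".
- Protocol 12.1: "a pregnancy test will be performed prior to enrollment and again at the last study visit (Day 270".
- SAP 9.5: "pregnancy test (at screening and final visit only".
- Protocol Table 3 and SAP 12.2 mark the test in the screening and Day 270 columns and nowhere else.

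The Table 3 row headed "Inclusion/Exclusion" is marked at screening and again at baseline, but no pregnancy test is marked at baseline, SRP, Day 1 or any dosing visit.

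Two footnotes to Table 3 fix the order of events before dosing: "Randomization occurs by IWRS after SRP has been completed", and "Product administration must occur within 3 days of the last SRP visit". Footnote a also allows a late final session: "The last SRP may occur on Visit 3/3b, or as an Unscheduled Visit". Dosing in all groups runs from Day 1 to Day 240 (protocol 7.3).

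Between the two tests the plan relies on other measures. Inclusion criterion 11 reads "For women with reproductive potential, willingness to use highly effective contraception". Medical history is updated at every visit, including SRP and Day 1 (Table 3; protocol 9.5 and 12.1.1). Protocol 12.5.4 tells subjects to report a suspected pregnancy and stops treatment at once if there is one. Subjects who leave early have the Day 270 assessments, which include the test (protocol 8.4).

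**The concern.** An exclusion criterion protects a subject only if it is known to hold when exposure starts. Here the one measurement behind the pregnancy exclusion may be weeks old by Day 1, and nothing after it is a test. The protocol treats exposure in pregnancy as important: treatment stops, the subject is withdrawn and the pregnancy is followed to term (12.5.4). Yet no scheduled test supports that stop rule until dosing is over.

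At stake is a pregnancy that began after screening and that neither the subject nor the site suspects. Followed as written, the plan would start and continue dosing until someone suspected it. Doses are most frequent just after Day 1, when the screening result is already old.

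**Working it through.** The documents state no figure for the age of the test at first dose, so there is none to reproduce. It follows from the Table 3 windows.

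**1. Age of the screening result at first dose**

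- Screening to baseline: at most 30 days.
- Baseline to SRP: at most 10 days.
- Last SRP to first dose: at most 3 days.
- Sum: 30 + 10 + 3 = 43 days.

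This is a maximum, and many subjects may be well below it. If baseline, SRP and first dose share a day, the maximum is 30 days. It can exceed 43 days, because no day limit is stated for a last SRP done as an Unscheduled Visit. The baseline eligibility re-check, which has no test, can precede Day 1 by 10 + 3 = 13 days.

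**2. Position of the second test**

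The last dose is Day 240 ± 7 and the final visit is Day 270 ± 7. The smallest gap is (270 − 7) − (240 + 7) = 263 − 247 = 16 days, so for a subject who completes the study this test always follows dosing. With the first dose 43 days after screening, nominal Day 270 is 43 + 269 = 312 days after the screening test.

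**3. Number of doses (protocol 7.3)**

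- Group 1: Days 1–5 and 8–12 = 10; Days 22, 30 and 60 bring this to 13 before Day 90; Days 90, 120, 150, 180, 210 and 240 add 6; total 19.
- Group 2: twice weekly for 12 to 13 weeks = 24 to 26; five monthly doses; total about 29 to 31.

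**4. Exposure if a pregnancy is present at Day 1**

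Volume per dose is 20 µL per tooth. At 18 teeth (the inclusion minimum) this is 0.36 mL; at 28 teeth (assumed upper count) it is 0.56 mL. How long the pregnancy stays unsuspected after Day 1 is also an assumption, so a range is shown.

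| Unsuspected after Day 1 (assumed) | Group 1 doses | Group 1 volume (mL) | Group 2 doses | Group 2 volume (mL) |
|---|---|---|---|---|
| 0 weeks | 0 | 0 | 0 | 0 |
| 2 weeks | 10 | 3.60–5.60 | 4 | 1.44–2.24 |
| 4 weeks | 11 | 3.96–6.16 | 8 | 2.88–4.48 |
| 6 weeks | 12 | 4.32–6.72 | 12 | 4.32–6.72 |

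Each volume is doses × 0.36 to doses × 0.56; for example, 12 × 0.56 = 6.72 mL. Group 3 receives no ST266.

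**5. What the documents do not give**

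They give neither the number of women of child-bearing potential nor any reproductive-risk data for ST266, so an expected number of exposed pregnancies cannot be computed.

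**The case against.** The strongest reply is that the plan already has layered protection and that test frequency is a matter of judgment. Contraception is an entry condition, eligibility is checked again at baseline, and history is taken at 19 or about 30 in-office treatment visits. Protocol 12.5.4 names a missed or late period as a reason to call, so a pregnancy that began soon after screening might be suspected before Day 1. Exposure is topical and under 1 mL a day. Enrollment had already begun (protocol 7.2 refers to current enrollment trends), so a change reaches only part of the trial.

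Much of this stands. It is why the exposure range must start at zero and why the consequence is modest. It does not close the gap: apart from the entry condition on contraception, which asks for willingness, these measures work only once someone is aware of a possible pregnancy.

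A reader might go further than the documents allow in four ways:

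- *That the documents contradict each other on testing.* They do not. Section 12.1 is only less specific about the timing of the first test.
- *That ST266 is shown to be hazardous in pregnancy.* Nothing in the documents says so.
- *That the efficacy result is at risk.* The testing schedule does not enter the efficacy analysis.
- *That a Day 90 test is needed as much as a pre-dose test.* It would precede only 6 of 19 Group 1 doses and at least 5 Group 2 doses, so it adds much less.

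**Conclusion.** The concern holds as a modest safety gap with a cheap remedy. No scheduled test would detect an unsuspected pregnancy between screening and the last dose, except in a subject who leaves early and is tested at exit. For a pregnancy present at Day 1, avoidable exposure lies between near zero and about 12 doses (up to about 6.7 mL). The upper end rests on two assumptions, 6 unsuspected weeks and 28 teeth, and applies only to Groups 1 and 2. The 43 days is the limit of the stated windows and not a typical value. The window and dose arithmetic is firm; how often such a pregnancy would occur cannot be judged from the documents.

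**What to change.** For women of child-bearing potential, add a urine pregnancy test at the last SRP visit, read before IWRS randomization. A subject who is positive is not randomized. Tie the test to the last SRP session and not to the Visit 3 column, so that it also applies when that session is an Unscheduled Visit. The result is then at most 3 days old at the first dose, compared with up to 43 days or more now.

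Suggested addition to 12.1.6.3: *Females of child-bearing potential will also have a urine pregnancy test at the last SRP visit, with the result read before randomization. A subject with a positive result will not be randomized.* Make the matching change in protocol 12.1 and Table 3 and in SAP 9.5 and 12.2.

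Testing before randomization matters because the ITT population is all randomized subjects (SAP 4). A woman found pregnant after randomization but before dosing would stay in that population even if she were replaced under protocol 9.4.

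A Day 90 test on urine already collected, read before any dose that day, is an optional addition of lower value.

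**Cost.** About one commercial urine test per woman of child-bearing potential who reaches SRP: roughly 150 or fewer, plus any who test positive or are replaced. If 20 to 40% of 150 subjects are in this group (assumed), that is 30 to 60 tests. No new visit, staff or invasive procedure is needed.

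**Downsides.** IRB approval is required before use (protocol 14.3), and only subjects not yet randomized benefit. A urine test may miss a very recent conception. There is still no scheduled test in the dense dosing phase between Day 1 and Day 90 (13 Group 1 doses, about 24 to 26 Group 2 doses), where detection continues to rest on history review and self-report.

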### **12.2. Adverse and Serious Adverse Events**

#### **12.2.1. Introduction**

This section defines the types of AEs and outlines the procedures for appropriately collecting, grading, recording, and reporting them. Information in this section complies with Title 21 Code of Federal Regulations (CFR) Part 312, International Conference on Harmonisation (ICH) Guideline E2A: Clinical Safety Data Management: Definitions and Standards for Expedited Reporting, and ICH Guideline E6: Good Clinical Practice: Consolidated Guidance.

The investigator is responsible for the detection and documentation of AEs regardless of treatment group or suspected causal relationship to the investigational product. For all AEs, the investigator must pursue and obtain information adequate to determine the outcome of the AE and to assess whether it meets the criteria for classification as a SAE requiring immediate notification to the sponsor or its designated representative.

#### **12.2.2. Adverse Event (AE)**

An AE is defined as any untoward or unfavorable medical occurrence associated with the subject's participation in the research, whether or not considered related to the subject's participation in the research. Any medical condition that is present at the time that the subject is screened will be considered as medical history and not recorded as an AE; however, if the condition worsens at any time during the study, it will be recorded and reported as an AE.

All AEs that occur after any subject signed consent, before treatment, during treatment, or within 30 days following the last final dose of treatment, whether or not they are related to the study, must be recorded.

#### **12.2.3. Serious Adverse Event (SAE)**

An AE is considered "serious" if, in the view of either the investigator or the sponsor, it results in any of the following outcomes (21 CFR 312.32(a)):

- Death: A death that occurs during the study or that comes to the attention of the investigator during the protocol-defined follow-up period must be reported to the Sponsor whether it is considered treatment related or not.
- Is life-threatening: An AE or suspected adverse reaction (SAR) is considered “life-threatening” if, in the view of either the investigator or the sponsor, its occurrence places the participant at immediate risk of death. It does not include an AE or SAR that, had it occurred in a more severe form, might have caused death.
- In-patient hospitalization or prolongation of existing hospitalization. Planned hospitalization or planned prolonged hospitalization do not fulfill the criteria for being an SAE, but should be documented in the subject’s medical record. Additional details further defining hospitalization criteria can be found in the Clinical Procedures Manual.
- Persistent or significant incapacity or substantial disruption of the ability to conduct normal life functions.
- Congenital anomaly or birth defect.

Or

- Is a medically important condition, i.e., events that may not be immediately life threatening or result in death or hospitalization but may jeopardize the subject or may require intervention to prevent one of the other outcomes listed in the definition above. Examples are intensive treatment in an emergency room or at home for allergic bronchospasm, blood dyscrasias, and convulsions that do not result in hospitalization, development of drug dependency, or drug abuse.

All SAEs that occur after any subject has signed consent, before treatment, during treatment, or within 30 days following the final dose of treatment, whether or not they are related to the study, must be recorded.

If an event meets any of the above definitions, regardless of the severity or relationship of the event to the study product, the event must be reported to the sponsor as described in Section [12.5.1](#).

#### **12.2.4. Severity of AEs/SAEs**

The study site will grade the severity of AEs experienced by study participants according to the following criteria:

- Mild (awareness of sign or symptom, but easily tolerated)
- Moderate (discomfort sufficient to cause interference with normal activities)
- Severe (incapacitating, with inability to perform normal activities)
- Life-threatening

**Note:** The terms serious and severe are not synonymous. Serious criteria as defined in Section [12.2.3](#) above serve as a guide for defining regulatory reporting obligations. The term severe is often used to describe the intensity (severity) of a specific event (as in mild, moderate,

or severe headache); the event itself, however, may be of relatively minor medical significance. This is not the same as serious, which is based on patient/event outcome or action criteria usually associated with events that pose a threat to a patient’s life or functioning. Therefore, an AE of severe headache might not be considered serious, but a moderate infection for which a subject is hospitalized should be reported as an SAE.

### 12.3. Relationship to Study Drug and Expectedness

An investigator who is qualified in medicine must make the determination of relationship to the investigational product for each AE (not related, possibly related, or definitely related). The investigator should decide whether, in his or her medical judgment, there is a reasonable possibility that the event may have been caused by the investigational product. If no valid reason exists for suggesting a relationship, then the AE should be classified as “not related.” If there is any valid reason, even if undetermined, for suspecting a possible cause-and-effect relationship between the investigational product and the occurrence of the AE, then the AE should be considered “related.”

If the relationship between the AE/SAE and the investigational product is determined to be “possibly” or “definitely,” the event will be considered to be related to the investigational product for the purposes of expedited regulatory reporting.

The sponsor’s determination of attribution will be used for reporting to the appropriate health authorities. The relation of an AE to study participation will be determined using the descriptors and definitions provided in Table 6. Additionally, in this study there are no suspected SAEs and all SAEs will be considered suspected unexpected serious adverse reactions (SUSARs).

**Table 6: Attribution of Adverse Events**

Not related	The AE is clearly not related.
Possibly related	The AE has a reasonable possibility to be related; there is evidence to suggest a causal relationship.
Definitely related	The AE is clearly related.

### 12.4. Collection and Recording Adverse Events

#### 12.4.1. Period of Collection

All AEs and SAEs will be collected from the time the informed consent is signed until the end of the study. All AEs and SAEs that occur after any subject has signed consent, before treatment, during treatment, or within 30 days following the final dose of treatment, whether or not they are related to the study, must be recorded.

##### 12.4.1.1. Methods of Collection

Adverse events may be collected as follows:

- Observing the participant

- Questioning the participant in an unbiased and non-leading manner
- Receiving an unsolicited complaint from the participant

An abnormal value or result from a clinical or laboratory evaluation can also indicate an AE if it is determined by the investigator to be clinically significant. If this is the case, it must be recorded in the source document and as an AE on the appropriate AE form(s). The evaluation that produced the value or result should be repeated until that value or result returns to normal or is stable, establishing a new baseline and the participant's safety is not at risk.

An abnormal laboratory value recorded at screening is not considered an AE, but is treated as a preexisting condition and should be recorded in the subject's medical history.

#### **12.4.2. Recording Method**

##### **12.4.2.1. Adverse Events**

Throughout the study, the investigator will record AEs on the appropriate eCRF regardless of their severity or relation to the study product. The investigator will treat participants experiencing AEs appropriately and observe them at suitable intervals until their symptoms resolve or their status stabilizes.

Once recorded, an AE will be followed until it either; resolves with or without sequelae, the subject ends study participation, 30 days after the final dose of study treatment, or 30 days after the subject prematurely withdraws (without withdrawing consent) or is withdrawn from the study, whichever occurs first.

